10.1 Statistical and Analytical Plans (SAP)

Due to the urgent COVID-19 crisis, there is no formal SAP.

10.2 Statistical Hypotheses

The null hypothesis for the registry study is that there are no significant associations between clinical characteristics at study entry and subsequent occurrence of cardiac dysfunction, lung dysfunction or death in hospitalized patients with COVID-19 infection.

There will be no hypothesis testing for the interventional trial. The primary endpoint is safety of AT-001 based on descriptive statistics and qualitative evaluation of adverse event monitoring. Descriptive statistics will be used to assess frequency of secondary endpoints without hypothesis testing.

10.3 Analysis Datasets

The registry dataset consists of all subjects with any entered data. The interventional safety data set will be all subjects who received at least one dose of AT-001

10.4 Description of Statistical Methods

10.4.1 General Approach

Descriptive statistics will be used to define data missingness, data distributions.

10.4.2 Analysis of the Primary Efficacy Endpoint(s)

Registry Study

CONFIDENTIAL This material is the property of the NYU School of Medicine and Langone Medical Center. Do not disclose or use except as authorized in writing by the study sponsor Interventional Template Version: 11 January 2019

- Multivariable logistic regression models and Cox Proportional Hazard models will be used to estimate the association between clinical variables at time of hospital admission and ICU admission with proportion of patients with decreased left ventricular ejection fraction ≥10% and secondary endpoints cardiac structure and function.
- Multivariable mixed models will be used to estimate the association between serial measures of cardiac structure and function, need for mechanical ventilation, and in-hospital mortality.

Interventional Study

- Safety assessment of AT-001 based on reported adverse events
- Exploratory analyses with descriptive statistics to estimate effects of co-enrollment on safety outcomes
- Exploratory analyses with descriptive statistics to describe clinical outcomes in patients treated

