4.2 Study Endpoints

4.2.1 Primary Study Endpoints

Primary Endpoint for Registry Study: Proportion of subjects with decreased left ventricular ejection fraction $\geq 10\%$ from baseline at time of hospitalization

Primary Endpoint for Embedded Clinical Trial: Safety of AT-001 based on adverse events reporting

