5.1 Inclusion Criteria

Registry Study: In order to be eligible to participate in the registry study, an individual must meet all of the following criteria:

- 1. Age ≥18 years of age
- 2. Hospitalized at one of the participating NYULH locations
- 3. Confirmed COVID-19 infection

Interventional Study: In order to be eligible to participate in the registry study, and individual must meet all of the inclusion criteria of the registry study plus the following critieria:

- 1. Hospitalized at NYU Tisch or NYU Winthrop
- 2. History of diabetes mellitus or blood glucose measurement >126 mg/dl

AND

EITHER

CONFIDENTIAL

This material is the property of the NYU School of Medicine and Langone Medical Center. Do not disclose or use except as authorized in writing by the study sponsor

3. History of hypertension and/or ischemic heart disease and/or heart failure

OR

4. Other co-morbid condition that in the opinion of the PI increases risk of heart or lung injury related to the aldose reductase pathway

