7.3 Study Schedule

Registry Study: All clinically-derived data on the attached eCRF will be collected on a daily basis until hospital discharge, or first 30 days of hospitalization (whichever is shorter).

Interventional study: All clinically-derived data on the attached eCRF will be collected on a daily basis during IP administration, with safety monitoring continuing 30 days after last dose of IP. In additional the following study procedures will be performed:

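### ICU-admission variables are related to an LVEF fall measured from hospitalization, so for patients transferred to ICU later the predictors can post-date the outcome.

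*Combined protocol and SAP*

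**What the plan says.** For the registry, Section 10.4.2 plans logistic and Cox regression of "clinical variables at time of hospital admission and ICU admission" on the proportion of patients with an LVEF decrease of at least 10%, and on secondary measures of cardiac structure and function. The Protocol Summary has the same wording, and Section 10.4.3 applies the same analyses to the secondary endpoints.

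Section 4.2.1 defines the decrease "from baseline at time of hospitalization". The null hypothesis in Section 10.2 concerns "clinical characteristics at study entry and subsequent occurrence of cardiac dysfunction, lung dysfunction or death".

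ICU care is not a condition of registry entry. Section 5.1 asks for adult age, confirmed infection and "Hospitalized at one of the participating NYULH locations". On the analysis set, Section 10.3 says: "The registry dataset consists of all subjects with any entered data". Registry data are "collected on a daily basis until hospital discharge, or first 30 days of hospitalization", whichever is shorter (Section 7.3). On missing values, Section 10.4.1 says only: "Descriptive statistics will be used to define data missingness, data distributions". Section 10.1 states that there is no formal SAP.

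**The concern.** The plan names two predictor time points but one outcome, anchored to the earlier one. Nothing defines an ICU subset, a time zero for the ICU variables, a landmark or time-dependent covariates. Nothing requires the LVEF fall to come after ICU admission.

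For a patient who goes to ICU some days after hospital admission, a fall between the two dates counts as an outcome although the ICU variables were measured after it. If cardiac deterioration contributed to the transfer, those variables may partly be consequences of the fall. The estimated associations would then mix risk factors with markers of an event that has already happened. Section 3.2 makes predictive models of cardiac risk an objective, and a model containing such variables would look more predictive than it could be in use.

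**Working it through.** **There is no plan figure to reproduce.** Section 10.5 calls the 500 registry participants a convenience sample and gives no alpha, power, effect size or event rate. The check is mainly a comparison of timing.

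**1. Timing in the text.**
- Section 10.2: predictors at study entry, outcome afterwards.
- Section 4.2.1: outcome measured from hospitalization.
- Section 10.4.2: predictors at hospital admission and also at ICU admission.

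The first two agree. The third agrees with them for hospital-admission variables, and for patients admitted directly to ICU, where the two time points coincide. It does not agree for patients transferred later.

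**2. The possible readings of Section 10.4.2.**
- *One joint model.* Patients never in ICU have no ICU-admission values, so a complete-case fit is restricted to ICU patients. Falls before ICU admission still count.
- *Two models, one per time point.* The missing values disappear if the second model is limited to ICU patients, but falls before ICU admission still count.
- *ICU admission as a yes/no covariate.* Nobody lacks a value, but ICU status is then attributed to days before it was reached.

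Under every reading, a Cox clock from hospital admission includes the days a patient had to survive in hospital in order to reach ICU. That interval is immortal for death. It also becomes event-free for LVEF decline if earlier declines are dropped without moving time zero.

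**3. Size of the joint-model restriction.** The ICU share is not in the documents; assume 20-40%.
- Patients kept: 0.20 × 500 = 100 to 0.40 × 500 = 200. Patients without ICU values: 400 to 300.
- Section 10.5 allows up to 50 predictors: 500/50 = 10 patients per predictor in the full registry, against 100/50 = 2 to 200/50 = 4 in the restricted fit.
- The only rate in the documents is the 10-20% risk of cardiac complications in severe hospitalized cases (Section 2.1), a proxy for the LVEF endpoint. With it, events number 0.10 × 100 = 10 to 0.20 × 200 = 40, or 0.2 to 0.8 per predictor, if the rate is the same in ICU patients.

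**4. Share of declines before ICU admission (illustration).** Assume, for patients who go to ICU:
- 30-day decline risk r = 0.10 or 0.20 (the Section 2.1 proxy);
- constant decline hazard λ = −ln(1 − r)/30, so 0.003512 or 0.007438 per day;
- exponential time to ICU admission with mean m = 2 or 4 days (not in the documents);
- decline and ICU timing independent.

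The share of declines by day 30 that precede ICU admission is

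[λ/(λ + 1/m)] × [1 − exp(−30(λ + 1/m))] / r

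| r | m (days) | λ/(λ + 1/m) | 1 − exp(…) | Share |
|---|---|---|---|---|
| 0.10 | 2 | 0.003512/0.503512 = 0.006975 | 1.0000 | 0.070 |
| 0.10 | 4 | 0.003512/0.253512 = 0.013853 | 0.9995 | 0.138 |
| 0.20 | 2 | 0.007438/0.507438 = 0.014658 | 1.0000 | 0.073 |
| 0.20 | 4 | 0.007438/0.257438 = 0.028893 | 0.9996 | 0.144 |

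That is about 7-14%. The result depends mostly on the assumed ICU delay and little on the event rate. If declines prompt transfers, independence fails and the share would be higher.

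**The case against.** The wording is brief and may be innocent. Section 10.4.2 speaks of models in the plural, so separate models may be meant, or ICU admission may be a simple indicator. Complete-case deletion is nowhere stated. The registry is observational and a convenience sample, the stated aim of the regression is to estimate associations, and no conclusion of the interventional trial depends on it. Section 10.1 openly says there is no formal SAP. All of this stands, and it limits the weight of the point. It does not remove it, because the timing problem remains under each reading and no other section settles it.

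A reader might infer more than the documents support:
- *That the predictors exist only for ICU patients.* This is true of ICU-admission variables alone; hospital-admission variables can exist for everyone.
- *That the risk models could not be used at either time point.* A model with hospital-admission variables only has no such problem, and Section 10.4.2 allows one.
- *That cardiac deterioration is what sends patients to ICU.* The documents do not say so. Section 2.3 attributes deaths mainly to respiratory failure, with cardiovascular complications in a minority.

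The phrase in Section 4.2.1 could also mean a decline already present at admission relative to an older value. The outcome would then precede a later ICU admission more often, so that reading does not help the plan.

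A last objection concerns feasibility. Registry data come from the medical record (Section 7.1.1) and no echocardiography schedule is stated, so a fresh LVEF baseline before ICU admission cannot be required of everyone. This stands, and the fix allows for it.

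**Conclusion.** The concern holds for ICU-admission variables in patients transferred to ICU after hospital admission. For them, Section 10.4.2 lets predictors post-date the outcome, conflicts with the study-entry framing of Section 10.2, and leaves immortal time in a Cox analysis timed from hospital admission. Restriction of the analysis to ICU patients follows only if both sets of variables enter one model fitted to complete cases.

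The true size cannot be obtained from the documents. The 7-14% share is an illustration that rests on the proxy risk, the assumed 2-4 day mean to ICU admission and independence of the two timings. The 100-200 patients kept rests on the assumed 20-40% ICU share. The plan should be changed before the registry is analysed; the interventional safety analysis is not affected.

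**What to change.** State two models in Section 10.4.2 and the Protocol Summary.

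- **Model 1 (primary).** All registry patients, time zero at hospital admission, hospital-admission variables only.
- **Model 2.** Patients admitted to ICU, time zero at ICU admission, hospital- and ICU-admission variables. Count only LVEF decreases first recorded after ICU admission, and exclude patients whose decrease was already recorded. Keep the Section 4.2.1 baseline unless a pre-ICU LVEF is available, and report how many patients lack one.

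Alternatively, enter the ICU variables in the Cox model as time-dependent covariates that take effect at transfer. This does not repair the logistic model.

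Reword Section 10.2 so that each hypothesis names its own starting point, and apply the same rule to the secondary endpoints through Section 10.4.3.

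The cost is a smaller ICU model: at most 100-200 patients under the assumed ICU share, less those with an earlier decrease, so its predictor list must be much shorter than 50. Where a pre-ICU LVEF replaces the hospitalization baseline, the endpoint changes for that model and the report should say so. With chart data, a decrease first recorded in ICU may have begun earlier; Model 2 reduces this problem but does not eliminate it. No new data collection is needed.

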Population	All subjects hospitalized with COVID-19 infection hospitalized will be enrolled in the registry; a subgroup meeting specific entry criteria listed below will be enrolled in the open-label interventional trial			
Study Sites	NYU Langone Tisch Hospital (registry and embedded clinical trial)NYU Langone Brooklyn Hospital (registry only)NYU Langone Winthrop Hospital (registry and embedded clinicaltrial)Bellevue Hospital Center (registry only)			
Number of participants	500 registry subjects enrolled at all sites 20 interventional trial subjects at NYU Tisch Hospital and NYU Winthrop			
Description of Study Agent/Procedure	AT-001 is an investigational novel Aldose Reductase Inhibitor (ARI) in Phase 2/3 development in the US, Canada and Europe for treatment of Diabetic Cardiomyopathy. The US IND# is 136043. A full Investigational Brochure is for the ongoing Diabetic Cardiomyopathy program is attached to this protocol.			
Reference Therapy	Standard of care			
Key Procedures	Data extraction from electronic medical record Administration of AT-001 1500 mg twice daily for up to 14 days			

	Registry Study
Statistical Analysis	 Multivariable logistic regression models and Cox Proportional Hazard models will be used to estimate the association between clinical variables at time of hospital admission and ICU admission with proportion of patients with decreased left ventricular ejection fraction ≥10% and secondary endpoints cardiac structure and function. Multivariable mixed models will be used to estimate the association between serial measures of cardiac structure and function and inhospital mortality.
	Interventional Study
	 Safety assessment of AT-001 based on reported adverse events Exploratory analyses with descriptive statistics to describe clinical outcomes in patients treated with AT-001 plus standard of care

Schematic of Study Design

1 Key Roles

Name	Role	Appointment	Department	Site
[name]	Principal Investigator	NYU Grossman SOM	Department of Medicine	NYU Tisch
[name]	Co-Investigator	NYU Grossman SOM	Department of Medicine	NYU Tisch
[name]	Co-Investigator	NYU Grossman SOM	Department of Medicine	NYU Tisch
[name]	Co-Investigator	NYU Grossman SOM	Department of Medicine	NYU Tisch
[name]	Co-Investigator	NYU Grossman SOM	Department of Medicine	NYU Tisch
[name]	Co-Investigator	NYU Grossman SOM	Department of Medicine	NYU Tisch
[name]	Co-Investigator	NYU Grossman SOM	Department of Medicine	NYU Winthrop

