3.1 Primary Objective

- Registry Study: To characterize serial measures cardiac structure and function and in-hospital survival in hospitalized patients with COVID-19 infection
- Interventional Trial: To characterize safety of AT-001 in hospitalized patients with COVID-19 infection

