3.2 Secondary Objectives (if applicable)

- To develop predictive models of cardiac risk in hospitalized COVID-19 infection patients
- To assess safety of treatment with AT-001 plus standard of care on in-hospital survival in patients with COVID-19
- To characterize the effects of treatment with AT-001 plus standard of care on in-hospital mortality, progression of acute lung injury requiring mechanical ventilation, and serial measures of cardiac structure and function

4 Study Design and Endpoints

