5.5 Duration of Study Participation

Duration of study participation for the registry study is until hospital discharge, or up to 30 days, whichever is shorter.

Duration of study participation for the interventional study is up to 30 days after last dose of AT-001.

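### The only model that names in-hospital mortality is an unspecified mixed model, which fits a once-only terminal event poorly and leaves death, discharge and day-30 inpatients without defined handling

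*Combined protocol and SAP*

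**What the plan says.** Section 3.1 gives the registry's primary objective: "To characterize serial measures cardiac structure and function and in-hospital survival in hospitalized patients with COVID-19 infection". Section 10.2 includes death among the outcomes in the registry null hypothesis, which concerns characteristics at study entry. The registry's primary endpoint in section 4.2.1 is different: "Proportion of subjects with decreased left ventricular ejection fraction" of at least 10% from baseline. Mortality is not in the endpoint lists of sections 4.2.1 and 4.2.2.

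Mortality is named in one analysis only. Section 10.4.2 states: "Multivariable mixed models will be used to estimate the association between serial measures of cardiac structure and function, need for mechanical ventilation, and in-hospital mortality". The Protocol Summary has the same sentence without ventilation: "Multivariable mixed models will be used to estimate the association between serial measures of cardiac structure and function and inhospital mortality". The other registry models are introduced by "Multivariable logistic regression models and Cox Proportional Hazard models will be used to estimate the association between clinical variables at time of hospital admission", and the outcomes then listed are the ejection-fraction decrease and the cardiac structure and function endpoints, not death.

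On follow-up, section 5.5 states: "Duration of study participation for the registry study is until hospital discharge, or up to 30 days, whichever is shorter". Section 7.3 collects registry data daily "until hospital discharge, or first 30 days of hospitalization (whichever is shorter". The Protocol Summary instead gives a participant duration of up to 30 days after discharge, without separating registry from trial.

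Section 10.1 says that there is no formal SAP, and sections 10.4.1 and 10.4.5 only describe missingness. No section mentions competing events, censoring rules, truncation by death or joint modelling.

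**The concern.** Death occurs once per patient and ends the serial measurements. Discharge also ends them, and in the registry it ends observation altogether. A model linking serial measures to death therefore has to say which is the outcome, what happens to the series when the patient leaves, and what discharge means for the risk of in-hospital death. The plan says none of this, and the model it names does not supply the answers by default.

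At stake is the part of the primary objective that concerns survival. A comparison of cardiac trajectories between patients who later died and those who did not could be reported as if it showed how cardiac status predicts death. Its size could also be distorted if sicker patients leave the data earlier through death, or healthier ones earlier through discharge.

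**Working it through.** **No figure in the plan to reproduce.** The registry size of 500 is a convenience sample (section 10.5), given without a death rate, discharge rate, effect size, alpha or power. The check is a reading of the model sentence, then two illustrations in which every rate is an assumption.

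**1. Possible readings of the mixed-model sentence**

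- *Death as outcome, clustering within patient.* Each patient has at most one event, so there is no repeated response.
- *Cardiac measure as outcome, death as covariate.* Earlier measurements are conditioned on a later event. The result is a trajectory by eventual fate, with follow-up truncated by death, discharge or day 30. It is not risk of death given cardiac status.
- *Death as outcome, clustering within hospital.* With four hospitals (section 4.1) this is possible with one outcome per patient, but the plan does not state it or say how serial measures would enter.

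**2. Does truncation matter for the second reading?** The simulation used 500 patients, 25 replicates per scenario, a marker measured every 3 days, and a linear mixed model with random intercept and slope. Slopes are in marker SD per 10 days; the slope difference is died minus not died (Monte Carlo SE in brackets).

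| Exit depends on current true marker value? | Overall slope: model / truth | Slope difference: model / truth |
|---|---|---|
| No | -0.191 / -0.198 | -0.040 (0.033) / -0.027 |
| Death only | -0.184 / -0.198 | -0.263 (0.021) / -0.134 |
| Death and discharge | -0.258 / -0.196 | -0.302 (0.021) / -0.208 |
| Both, more strongly | -0.319 / -0.208 | -0.242 (0.015) / -0.260 |

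Where both exits depend on the marker, the overall slope is too steep by (0.258 - 0.196)/0.196 = 32% and (0.319 - 0.208)/0.208 = 53%. The slope difference is 0.263/0.134 = 1.96 times the truth with death-only dependence and 0.242/0.260 = 0.93 times with strong dependence. With no dependence the model is close to the truth. The died-versus-not difference in baseline level stays close throughout (for example -0.860 against -0.890). The mechanism is real, but conditional.

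**3. Why discharge needs its own place if absolute risk is reported.** Take constant daily hazards d (death) and q (discharge alive).

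- In-hospital death by day 30: d/(d+q) × [1 - exp(-30(d+q))]
- 1 minus Kaplan-Meier with discharge censored: 1 - exp(-30d)
- Still in hospital at day 30: exp(-30(d+q))

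With d = 0.015 and q = 0.08: 0.1579 × 0.9422 = 14.9%, against 1 - exp(-0.45) = 36.2%. With q = 0.04: 0.2727 × 0.8080 = 22.0%, again against 36.2%.

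| d | Risk by day 30 at q = 0.05 / 0.10 / 0.15 | Discharge censored |
|---|---|---|
| 0.005 | 7.3% / 4.6% / 3.2% | 13.9% |
| 0.01 | 13.9% / 8.8% / 6.2% | 25.9% |
| 0.02 | 25.1% / 16.2% / 11.7% | 45.1% |

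Over this grid the share still in hospital at day 30 runs from 0.6% to 19.2%, or about 3 to 96 of 500 patients whose status the plan does not define.

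A cause-specific hazard ratio alone does not determine the risk ratio. With d = 0.01, q = 0.10 and a death hazard ratio of 2, the 30-day risk ratio is 1.85, 2.37 or 2.86 when the same factor's discharge hazard ratio is 1, 0.7 or 0.5.

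**The case against.** The strongest reply is that this is under-specification and not demonstrated error. The protocol admits that it has no formal SAP, so silence on death and discharge does not show that they will be ignored. Other valid analyses also exist. A yes/no analysis of in-hospital death by day 30 treats discharge alive as a non-event and has no discharge-censoring problem. A cause-specific hazard ratio that censors discharge is a legitimate association. All of this stands, and it limits the point in four places where a reader might infer more:

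- *That the association is biased.* Not shown. It depends on the outcome chosen, the model form and whether exit depends on cardiac status.
- *That the plan will censor discharge and so inflate death risk.* Section 10.4.2 does not assign the Cox model to death, and no section promises absolute death risks. The 14.9% and 36.2% illustrate a hazard to avoid, not a planned result.
- *That mortality prediction is an objective.* Section 3.2 says "To develop predictive models of cardiac risk in hospitalized COVID-19 infection patients"; cardiac risk is not mortality.
- *That patients still in hospital at day 30 count as survivors.* No section says so; their status is undefined.

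The reply does not remove the core. The plan does name a method for mortality, and under the within-patient reading, with death as outcome or as covariate, that method does not give risk of death given cardiac status. The alternatives that would work are not in the plan.

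**Conclusion.** The point holds as a mismatch between the mortality question and the only model named for it, together with an undefined outcome and undefined handling of death, discharge and day-30 inpatients. It rests on sections 3.1, 10.2, 10.4.2, 5.5 and 7.3 and on the absence of any rule elsewhere. Bias is possible if exit depends on cardiac status, which is plausible because section 2.1 lists reduced contractile function and fatal circulatory collapse among the complications of severe infection. The documents fix neither its size nor its direction, and the simulated distortions and hazard figures depend entirely on assumed inputs. The ejection-fraction primary endpoint is outside this point. The change is worth making because a better-suited standard analysis is available on data already planned.

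**What to change.** In section 10.4.2 and the Protocol Summary:

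- Limit mixed models to describing cardiac trajectories.
- Define the mortality outcome as in-hospital death by day 30, with patients still in hospital at day 30 administratively censored (alive in hospital).
- Fit a cause-specific Cox model for death with the most recent cardiac measure and ventilation status as time-updated covariates, and a parallel model for discharge alive as the competing event.
- Report Aalen-Johansen cumulative incidence, not 1 minus Kaplan-Meier with discharge censored.
- State that the hazard ratios are associations and not absolute risks. If individual risk prediction from serial measures is wanted, use landmarking or a joint model, because Cox models with such time-updated covariates do not directly give it.
- Reconcile the participant duration in the Protocol Summary with section 5.5.

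The cost is analysis wording and somewhat more programming in standard software. No new data are needed, since section 7.3 already collects daily records to discharge or day 30. One limitation should be stated: the cardiac measures come from routine care, so the most recent value may be old, sparse or informatively timed.
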